11.3.1 Premature Discontinuation Description

For each premature discontinuation, the following parameters will be listed: participant number, dates of start and end of treatment, and the reason of premature discontinuation.

11.3.2 Safety

Adverse events (AEs) will be divided into pre-emergent and post-emergent AEs and presented separately as the number and percentage of subjects for each system organ class, preferred term, and lower level term. Furthermore, the lower level term, intensity, relationship, action taken, and outcome will be reported for each adverse event.

Continuous safety parameters (vital signs, anthropometrics, clinical chemistry, haematology) will be summarized with number of subjects, mean, standard deviation, median, minimum value, and maximum value for each measurement point.

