5 STUDY OBJECTIVES

The objective of this study is to investigate the efficacy of Nic's Ketogenic Diet on cardiovascular health and inflammation in healthy adults with mildly elevated LDL-C.

Primary outcomes:

The change in inflammation, as assessed by the change in erythrocyte sedimentation rate (ESR) and C-reactive protein (CRP) following Nic's Keto Diet for 140 days. The main outcome of the study is to investigate whether in periods of higher LDL there will be positive impacts on cardiovascular health and inflammation.

Secondary outcomes:

Changes to the following parameters from baseline to day 140 at monthly intervals following Nic's Keto Diet:

1. Weight
2. Blood pressure (BP)
3. Lipid panel

Changes to the following parameters from baseline to days 70 and 140 following Nic's Keto Diet:

1. Body composition (total body fat (%), android fat (%), gynoid fat (%), android/gynoid fat ratio, and muscle mass (%)) as assessed by DEXA Scan

[figure not shown]
Changes to the following parameters from baseline to day 140 following Nic's Keto Diet:

1. HbA1c
2. Fasting glucose
3. Free Tri-iodothyronine (T3)

Safety outcomes:

1. Incidence of pre-emergent and post-emergent adverse events
2. Electrocardiogram (ECG) after 70 and 140 days of following Nic's Keto Diet
3. Vital signs: heart rate (HR)
4. Anthropometrics: BMI calculation
5. Clinical chemistry: alanine aminotransferase (ALT), aspartate aminotransferase (AST), total bilirubin, creatinine, electrolytes (Na⁺, K⁺, Cl⁻, P), HbA1c, fasting glucose, and estimated glomerular filtration rate (eGFR))
6. Hematology: white blood cell (WBC) count with differential (neutrophils, lymphocytes, monocytes, eosinophils, basophils), red blood cell (RBC) count, hemoglobin, hematocrit, platelet count, RBC indices (mean corpuscular volume (MCV), mean corpuscular hemoglobin (MCH), mean corpuscular hemoglobin concentration (MCHC), red cell distribution width (RDW), and mean platelet volume (MPV))

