The total blood volume collection for the laboratory assessments listed above will be approximately 68 mL, over the period from screening to end of study (approximately 140 days). At any study visit, blood loss per volunteer is not expected to exceed 18 mL. Additional blood samples may be collected during the course of the study in order to perform or repeat laboratory tests outlined in the Schedule of Assessments if needed.

Dynacare Laboratory will be used in this study to measure blood parameters.

Urine pregnancy test will be performed at the KGK Science clinic site.

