10.2.2 Treatment and Follow-up of Laboratory Abnormalities

In the event of participant-initiated withdrawal or clinically significant unexplained abnormal laboratory test values, the participant will be withdrawn from the treatment and will remain in the study and be required to attend all remaining study visits as part of a safety arm.

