11.2 Analysis Plan

The **Safety Population** will consist of all participants who start the diet, and on whom any safety information is available.

The **Intent-to-Treat (ITT) Population** will consist of all participants who start the diet and on whom efficacy information is available.

The **Per Protocol (PP) Population** will consist of all participants who comply with the diet, do not have any major protocol violations and complete all study visits and procedures connected with measurement of the primary variable.

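### Continuous safety summaries can mix on-diet and off-diet values, because participants withdrawn from the diet keep attending and section 11.3.2 makes no split by diet status

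*Combined protocol and SAP*

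**What the plan says.** Section 10.2.2 applies "In the event of participant-initiated withdrawal or clinically significant unexplained abnormal laboratory test values". The person comes off the diet but "will remain in the study and be required to attend all remaining study visits as part of a safety arm". Section 7.4 describes withdrawal differently: it speaks of leaving the study, with end-of-treatment assessments done at that point where feasible.

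Section 11.2 defines the Safety Population as "all participants who start the diet, and on whom any safety information is available". Section 11.3.2 then gives one descriptive summary per measurement point: "Continuous safety parameters (vital signs, anthropometrics, clinical chemistry, haematology) will be summarized with number of subjects, mean, standard deviation", plus median, minimum and maximum. Section 11.3 rules out imputation for this population, so the summaries use observed values.

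No section defines the safety arm as an analysis group, splits safety values by diet status, or asks for a last or worst on-diet value.

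The schedule (1.3, 9.3 to 9.6, 9.9) places CBC, electrolytes, creatinine, eGFR, AST, ALT and total bilirubin at screening and Visit 8 only. Visits 3 to 7 draw a lipid panel. Section 9.9 adds: "Additional blood samples may be collected during the course of the study in order to perform or repeat laboratory tests". For each early stop, section 11.3.1 lists the "dates of start and end of treatment" and the reason.

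**The concern.** Read together, these sections put a participant who stopped the diet weeks before Visit 8 in the same Day 140 row as participants still following it. One trigger for stopping is an abnormal laboratory value, so the mixing is not random with respect to safety. If such values return towards normal after stopping, the Day 140 mean, SD and maximum can look unremarkable for the very reason that a problem was found and acted on.

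The schedule sharpens this for haematology and most clinical chemistry. Visit 8 is the only scheduled draw after the diet starts, so a participant off diet by then has no scheduled on-diet value. An on-diet value would have to come from an additional sample or from a withdrawal assessment under 7.4, and no rule says whether or where either enters the summary.

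At stake is whether the continuous tables can be read as describing safety on the diet. Section 5 words at least one safety outcome in those terms: "Electrocardiogram (ECG) after 70 and 140 days of following" the diet.

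**Working it through.** The plan has no figure of its own to reproduce. Section 11.1 sets 14 participants without a calculation, and no withdrawal rate is given. The number off diet, the recovery fraction and the laboratory values below are therefore assumptions, shown over a range.

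**Step 1. Which rows can be mixed.**

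| Parameter | Scheduled values after the diet starts | Rows that can mix diet status |
|---|---|---|
| CBC, electrolytes, creatinine, eGFR, AST, ALT, bilirubin | Visit 8 only | Day 140 |
| Vital signs, BMI | Visits 3 to 8 | Visits 3 to 7 and Day 140 |

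**Step 2. Dilution of a shift common to all participants.** Let *k* of 14 be off diet at Day 140, all 14 attend, and each off-diet value have reversed by fraction *r* of the shift. The pooled mean then shows

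retained share = 1 − *k* × *r* / 14.

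| *k* | Off-diet share (*k*/14) | *r* = 0 | *r* = 0.5 | *r* = 1 |
|---|---|---|---|---|
| 1 | 7.1% | 100% | 96.4% | 92.9% |
| 2 | 14.3% | 100% | 92.9% | 85.7% |
| 3 | 21.4% | 100% | 89.3% | 78.6% |
| 4 | 28.6% | 100% | 85.7% | 71.4% |

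If a value worsens after stopping, *r* is negative and the pooled mean overstates the on-diet shift. For example, *k* = 2 and *r* = −0.5 give 1 + 2 × 0.5/14 = 107.1%.

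**Step 3. Harm confined to those withdrawn.** Assume 12 participants at 25 units and 2 at 90 units when they stop.

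- Last on-diet value for everyone: (12 × 25 + 2 × 90)/14 = 480/14 = 34.3, maximum 90.
- Pooled Day 140, full recovery to 25: (14 × 25)/14 = 25.0, maximum 25.
- Pooled Day 140, half recovery to 90 − 0.5 × 65 = 57.5: (12 × 25 + 2 × 57.5)/14 = 415/14 = 29.6, maximum 57.5.
- Pooled Day 140, no recovery: 34.3, maximum 90. Nothing is lost.
- Day 140 restricted to those on diet: mean 25, maximum 25, n = 12.

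The last line shows that removing off-diet values does not bring the signal back. Only a last or worst on-diet value does. For a chemistry or haematology parameter, the value of 90 must come from an additional sample or a withdrawal assessment, because no panel is scheduled between screening and Visit 8.

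**Step 4. How likely any mixing is.** With an assumed off-diet probability *d* per participant, independent across participants, P(at least one) = 1 − (1 − *d*)^14.

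| *d* | Expected number (14 × *d*) | P(at least one) |
|---|---|---|
| 10% | 1.4 | 77% |
| 20% | 2.8 | 96% |
| 30% | 4.2 | 99% |

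These are chances that someone is off diet. They are not chances that harm is masked, which also requires attendance at Day 140 and reversal.

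**The case against.** A reader might infer that recovered off-diet values will be reported as Day 140 diet safety and that harm is therefore understated. The documents do not support that. It needs someone to stop early, attend Visit 8 and have a value that has reversed, and the plan establishes none of these. With no reversal there is no understatement, and with worsening after stopping the error runs the other way.

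Four further points count against a strong reading.

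- **Events stay visible.** Under 10.1.4 a clinically significant laboratory result that leads to stopping the diet is recorded as an adverse event. Section 11.3.2 reports action taken and outcome for each event, and 11.3.1 lists each discontinuation. With 14 participants these individual records carry much of the signal. This stands and limits the point to the continuous summaries. It does not remove it: a participant who stops by choice need have no adverse event, and shifts in heart rate, BMI or laboratory values below clinical significance would appear only in those summaries.
- **The pooling is inferred.** It follows from the Safety Population definition and the lack of a split; no sentence states it. The word arm is compatible with separate presentation, and keeping all starters is a sound safety convention. This stands as to wording, but an analyst following section 11 literally would pool.
- **The schedule limits the laboratory mechanism.** An abnormal ALT first seen at Visit 8 leaves no later visit at which a recovered value could replace it. This stands. The same schedule is also why a participant already off diet may have no on-diet panel at all.
- **ECG lies outside the quoted summary.** The sentence in 11.3.2 does not list ECG. The ECG outcome shows only that on-diet safety was of interest.

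**Conclusion.** The point holds in conditional form. As written, the Day 140 continuous safety rows, and vital signs and BMI at Visits 3 to 7, can contain an unlabelled mixture of on-diet and off-diet values, and for the Visit 8-only panel an off-diet participant may contribute no on-diet value.

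The size depends on quantities the plan does not give. For 1 to 4 participants off diet, the retained share of a common shift runs from 92.9% down to 71.4% with full reversal, and stays at 100% with none. Where harm is confined to those withdrawn and has fully reversed, mean and maximum can both look normal. All of this assumes that those off diet attend Visit 8.

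A change is worth making before analysis, because the mixture cannot be read as safety on the diet whichever way the error runs. It is not evidence that harm will go unreported. The adverse event and discontinuation outputs remain in place.

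**What to change.** 1. In 11.2, state what the safety arm is for analysis. Keep all starters in the Safety Population.
2. In 11.3.2, flag each safety value as on-diet or off-diet from the treatment end dates already listed under 11.3.1, and present continuous parameters by that flag at each measurement point.
3. Add each participant's last and worst on-diet value for every continuous safety parameter, including additional, repeat and withdrawal-visit samples, with the number of on-diet samples behind it. This carries the fix: an on-diet-only Day 140 row is selected towards those who tolerated the diet and, in the example above, still shows a mean and maximum of 25. Read worst values descriptively, since people sampled more often have more chances of an extreme value.
4. Apply the same flag to ECG results and adverse events.
5. Sections 7.4 and 10.2.2 must be reconciled on whether a withdrawn participant leaves or stays, and the plan should say in which row withdrawal-visit values are placed. This is for the sponsor and investigator to settle; no clinical rule is proposed here.

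The cost is analysis-plan wording, one derived flag from dates already recorded and a few more table rows. No new data are needed. The drawback is a smaller n in the on-diet rows, for example 12 of 14 if two have stopped.

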9 STUDY ASSESSMENTS

9.1 Visit 1 – Screening (Day -45 to Day -1)*

** At the discretion of the Qualified Investigator, any participants falling outside of the screening window (Day -45 to Day -1) due to scheduling issues will be asked to repeat eligibility/screening procedures prior to baseline visit.*

At screening, an informed consent form will be given to the potential volunteer. They will be required to read the information and will be given the opportunity to seek more information if needed, or have the option to take the consent form home to review prior to making their decision. If agreeable, the volunteer will sign the consent form and receive a duplicate of the signed copy. Once consent has been obtained, the screening visit will proceed following a prior 12-hour fast. Each volunteer will be sequentially assigned a screening number to be entered in the screening and enrollment log.

Screening assessments include:

1. Review of medical history and current health status
2. Assessment of inclusion and exclusion criteria
3. Review of concomitant prescribed and over-the-counter (OTC) medications, supplements, foods, and drinks (concomitant therapies)
4. Urine pregnancy test for female potential participants that are of child-bearing potential
5. Height and weight measurements and BMI calculation (Section 9.5.1)
6. Seated resting blood pressure and heart rate measurements (Section 9.5.2)
7. Collection of fasted blood samples for the analysis of complete blood count (CBC), electrolytes (Na⁺, K⁺, Cl⁻, P), HbA1c, glucose, eGFR, creatinine, AST, ALT, and total bilirubin, lipid panel and TSH level analysis
8. Dispense 3-day food records and instruct participants on completion and provide nutrition counselling

The next visit will be scheduled for potentially eligible participants for their baseline visit.

Reminders for participants prior to their next in-clinic visit:

1. Return to the clinic in a 12-hour fasted state
2. Complete 3-day food records
3. Abide by instructions for medications as per Section 7.3.1 and OTC medications, supplements, and food and drinks as per Section 7.3.2.
4. Maintain similar levels of physical activity

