11 STATISTICAL EVALUATION

11.1 Determination of Sample Size

Because this is a pilot study to explore the efficacy and safety of Nic's Ketogenic Diet, sample size will not be calculated. A total of 14 participants will be enrolled.

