11.3 Statistical Analysis Plan

All test of significance will be performed at 2-sided, alpha level = 0.05 unless otherwise specified.

All the primary and secondary endpoints will be analysed as continuous variables.

For each primary and secondary endpoint, descriptive statistics including number of subjects, arithmetic mean, standard deviation, median, minimum and maximum values will be presented for each study day and for the changes from baseline (Day 0) to each subsequent study day.

Changes in continuous endpoints from baseline will be calculated as:

$$\text{Change to } V_i = \text{Value at } V_i - \text{Value at } V_{\text{baseline}}$$

The continuous endpoints will be analysed with Mixed Model for Repeated Measures (MMRM). The model will include baseline value and visit as independent variables. P-values for the changes from baseline will be obtained from the model. No adjustment on p-values for multiple primary endpoints will be made.

Missing data for the primary and secondary endpoints will be imputed with last-observation-carried-forward (LOCF) method or multiple imputation as a sensitivity analysis for ITT Population. No imputation will be performed for PP and Safety Population.

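### Section 11.3.2 summarises safety-only parameters visit by visit, with no within-person change or reference-range shift, and plans no analysis of the ECG

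*Combined protocol and SAP*

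**What the plan says.** Section 11.3.2 has two parts. Adverse events are tabulated by class and term, and the details of each event are reported. Four named groups of continuous safety parameters are summarised by number of subjects, mean, standard deviation, "median, minimum value, and maximum value for each measurement point".

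Section 11.3 gives primary and secondary endpoints something further: descriptive statistics at each study day and "for the changes from baseline (Day 0) to each subsequent study day". Section 11.3.2 has no matching sentence. Section 11.3 also rules out imputation for the Safety Population.

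Section 5 lists, as the second safety outcome, "Electrocardiogram (ECG) after 70 and 140 days of following" the diet. The schedule in Section 1.3 places the ECG at Visits 2, 5 and 8.

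The main safety laboratory panel is drawn at screening, where Section 9.1 lists "Collection of fasted blood samples for the analysis of complete blood count (CBC" and the chemistry tests, and again at Visit 8. On size, Section 11.1 says "A total of 14 participants will be enrolled", and Section 7.4 says that leavers are not replaced.

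**The concern.** Section 11.1 describes a pilot that explores safety as well as efficacy. In a group this small, the useful safety questions concern individuals: how far did each person move, and how many went from normal to abnormal? A row of summary statistics at screening beside another at Day 140 does not answer them, because it does not link the two values from the same person. If some people lack the later sample, the two rows also describe different people.

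The ECG gap is simpler. Tracings would be taken for a stated safety outcome, in a trial about cardiovascular health, with no rule for summarising them. What gets reported would then be decided after the results are known.

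**Working it through.** The plan gives no figure to reproduce, since Section 11.1 states that "sample size will not be calculated". The check is a cross-reading followed by an illustration.

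**Step 1. Which parameters lack a change summary?** Sources: Sections 1.3, 5, 9.1 to 9.6, 9.9 and 11.3.

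| Parameter | Values scheduled | Change summary planned? |
|---|---|---|
| Blood pressure, weight | Every visit | Yes, as secondary outcomes |
| HbA1c, fasting glucose | Visits 1, 2 and 8 | Yes, as secondary outcomes |
| BMI | Every visit | Not named; height is measured once, so BMI change is weight change rescaled |
| Heart rate | Every visit | No |
| Haematology, electrolytes, AST, ALT, bilirubin, creatinine, eGFR | Visits 1 and 8 | No, and no Day 0 value exists |
| ECG | Visits 2, 5 and 8 in the schedule; Visits 5 and 8 in the visit lists | No, and no per-visit summary either |

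**Step 2. Is the ECG covered elsewhere?** The governing sentence reads "Continuous safety parameters (vital signs, anthropometrics, clinical chemistry, haematology) will be summarized with number of subjects, mean, standard deviation, median, minimum value, and maximum value". Its bracket names four groups, and the ECG is not among them. Section 9.7.4 covers only how the tracing is taken. No other section says how it is read, classified or summarised. With full attendance this concerns 14 × 3 = 42 tracings on the schedule, or 14 × 2 = 28 on the visit lists.

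**Step 3. Can the planned row hide a change?** Assumed values, arbitrary units, n = 14: 14, 16, 18, 19, 20, 21, 22, 23, 24, 25, 27, 29, 33, 38. The sum is 329 and the mean 329/14 = 23.5. SD is 6.6, median 22.5, range 14 to 38.

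- *(a) One person rises from 14 to 36 and nobody else changes.* The mean is (329 + 22)/14 = 25.1, up by 22/14 = 1.6. SD is 6.8, median 23.5, range 16 to 38. The maximum is unchanged and nothing in the row points to the rise. A paired summary shows a median change of 0 and a maximum change of +22.
- *(b) Everyone rises by 3, and the two highest (33 and 38) have no later value.* The later mean is (329 − 71)/12 + 3 = 24.5. The per-visit means differ by 24.5 − 23.5 = +1.0, while the paired change is +3.0. The medians differ by 24.5 − 22.5 = +2.0.
- *(c) One person rises from 14 to 90.* The mean is (329 + 76)/14 = 28.9 and the maximum is 90. The planned row shows this.

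The documents give no dropout rate, so (b) is shown over a range. If the k highest are missing, the difference in means is:

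| k missing | 0 | 1 | 2 | 3 | 4 |
|---|---|---|---|---|---|
| Difference in means | +3.0 | +1.9 | +1.0 | +0.3 | −0.3 |
| Paired change | +3.0 | +3.0 | +3.0 | +3.0 | +3.0 |

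For k = 4, for example, (329 − 127)/10 + 3 − 23.5 = −0.3. Losing the highest values is the unfavourable case; if leavers are typical of the group, the bias is small.

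**The case against.** A reader might infer that the plan reports only group means. It does not. The planned row also holds n, SD, median, minimum and maximum. A large outlier appears in the maximum, as in (c). In (b), n falls from 14 to 12, the maximum falls from 38 to 32 and the median moves by 2.0, so a careful reader has warning that the group has changed.

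A reader might also infer that individual harm has no route into the report. Section 10.1.4 sends clinically significant laboratory abnormalities to the adverse event form, with AST or ALT above twice the upper limit of normal as its example, and Section 11.3.2 then reports each event. An ECG finding could likewise be recorded as an adverse event if the investigator judged it to be one.

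A third inference is that the Day 140 row holds completers only. Section 10.2.2 keeps participants who withdraw themselves, or who have unexplained clinically significant results, attending the remaining visits. Section 7.4 asks for end-of-treatment evaluations at withdrawal where possible, and Section 11.3.1 lists each discontinuation with its reason. These reduce the dropout problem.

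Finally, Section 11.3 refers in places simply to continuous endpoints, which might be read to include safety parameters.

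What stands after all this: Section 10.1.4 expressly leaves out results that are outside the reference range but below its clinical significance criteria, and those are the movements a shift table counts. The retention rules reduce missing values without guaranteeing complete pairs. The broad reading of Section 11.3 does not rescue the laboratory panel, because its baseline is Day 0 and no Day 0 sample of that panel is drawn.

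**Conclusion.** The point holds in a limited form. Heart rate, haematology, electrolytes, liver tests and renal tests have per-visit summaries with no within-person change, shift table or threshold count. The ECG has no analysis. It is not true that safety measures in general lack change summaries: blood pressure, weight, lipids, HbA1c and fasting glucose have them as secondary outcomes.

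On size, one person is 1/14 = 7.1% of a mean (1/12 = 8.3% if two are missing). A rise of 22 units in one person can therefore appear as 1.6, and a uniform rise of 3.0 as 1.0 when the two highest values are lost. These figures rest on assumed laboratory values and assumed losses; they show that masking is possible, not that it is likely. The ECG omission needs no assumption.

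This should be corrected before the data are analysed. It does not affect the primary analysis.

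**What to change.** Amend Section 11.3.2 as follows.

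1. **Baseline.** Use Visit 1 (screening) for CBC, electrolytes, AST, ALT, bilirubin, creatinine and eGFR, and Day 0 for heart rate. Label the former as change from screening, since that sample may be taken up to 45 days before the diet starts.
2. **Paired change.** Summarise within-person change in participants with both values, and state how many pairs there are.
3. **Shift tables.** Cross-classify each laboratory test as below, within or above the reference range at baseline and at Visit 8. Add the count of participants above the AST/ALT level already named in Section 10.1.4.
4. **ECG.** First reconcile Section 1.3, which schedules an ECG at Visit 2, with the Section 9.2 procedure list, which omits it. Then define the reading categories (for example normal, abnormal not clinically significant, abnormal clinically significant) and tabulate shifts from baseline to Days 70 and 140.

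No significance tests are needed. The laboratory and heart-rate tables use values already scheduled. The cost is some analysis-plan wording, a few extra tables and agreed ECG categories. Whether the ECG needs any further collection depends on how the two Visit 2 lists are reconciled.
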